## 1. Purpose

**a) In layperson's language state the purpose of the study in 3-5 sentences.**

The purpose of this research is to study the effects of a novel combined software-hardware device built onto commercially available Google Glass technology that provides an automated emotion expression recognition system and face tracker to determine the effects of providing social cues to individuals with a diagnosis of ASD. This novel device will use a camera, microphone, and head motion tracker that will record the behavior of the subject during interactions with other people. The system is designed to give participants non-interruptive social cues in real-time and will record social responses that can later be used to help aid behavioral therapy.

**b) State what the Investigator(s) hope to learn from the study. Include an assessment of the importance of this new knowledge.**

Investigators hope to learn the effects of this novel software-hardware device in terms of providing social cues to individuals with ASD. Refining and evaluating this system has implications to not only help aid behavioral interventions with individuals with ASD, but it also has broader implications on new forms of human-computer and human-human interaction. The system's ability to provide continuous behavioral therapy outside of clinical settings will enable dramatically faster gains in social acuity that may, within a limited and self-directed period of time, encourage the child to engage in more advanced social settings on his/her own.

**c) Explain why human subjects must be used for this project.**

Human subjects must be used for this project because the purpose of the study is to determine the efficacy of this novel device in social interactions for individuals with ASD. There are no suitable animal models for facial emotion recognition in ASD, nor are there comparable behavioral therapies for animals, and therefore, human subjects must be used.

## 2. Study Procedures:

Participants: Participants will be ages 6-12 years old. We anticipate recruiting up to 80 ASD participants. We will also be recruiting family members and friends of participants to consent to participate as "non-participants." The research staff will obtain informed consent before any study procedures begin. Consent and assent will be obtained either electronically or in-person.

For n=50 participants, we will run a cross-over design study where 25 participants will randomly be assigned to group one and continue treatment as usual (control), or group two and continue treatment as usual plus study procedures (treatment). For these 50 participants, they must receive ABA therapy in the home at least 2xs/week. We will try to understand the efficacy of the device in comparison to ABA therapy.

The procedures for the "treatment" group are as follow:

1/ complete screening questionnaires and phone screen  
2/ come in for onboarding session (as described above) and take device home to use for 6 weeks. They will use the device at least 4xs/week for 20 minute sessions with either their parents or ABA therapist.

They will have phone calls with study managers to see how usage of the device at home is going.

3/ come in for conclusion (as described above) and return device  
4/ come in 6 weeks later for follow up (as described above)

During onboarding, conclusion, and follow-up, we will also conduct unstructured interviews to get feedback from research participants. At the end of the 12 week "treatment group" period and they complete the follow up, a \$50 Amazon gift card is provided as compensation for participation in the study.

The procedures for the "control" group are as follow:

1/ complete screening questionnaires and phone screen  
2/ come in for onboarding session (as described above)  
3/ come in for an appointment (appointment 1) 6 weeks after onboarding and conduct evaluations again. Participants will now take device home to use for 6 weeks. They will use the device at least 4xs/week for 20 minute sessions with either their parents or ABA therapist.  
They will have phone calls with study managers to see how usage of the device at home is going.  
4/ come in for conclusion (as described above) and return device  
5/ come in 6 weeks later for follow up (as described above)

During onboarding, appointment 1, conclusion, and follow-up, we will also conduct

unstructured interviews to get feedback from research participants. At the end of the 18 week "control group" period and they complete the follow up, we will provide to them a \$50 Amazon gift card.

Screening Questionnaire: We will send around a link to a redcap survey for all recruited participants from the recruitment website and with other recruitment efforts. We will ask interested participants to fill out the Screening Questionnaire. Our goal will be to determine eligibility based on location (needs to be local to Stanford), still interested in participating, has a child that meets our eligibility criteria, and a brief overview of the child. Eligible families will be contacted via email or phone to set up scheduling for in-lab study sessions. Parents will be asked to fill out these questionnaires no more than 4 times each (Baseline, at the end of the intervention, and at 6-weeks follow-up).

Standardized Behavioral and Clinical Characterization Scales, Checklists, and Measures:

*Clinical Phenotyping Measures Parents:* The Social Responsiveness Scale (SRS-2), The Vineland Adaptive Behavior Scale (VABS-2), Social Communication Questionnaire (SCQ), and Child Behavior Checklist (CBCL).

*Child:* Participants will also undergo the Abbreviated Battery IQ (ABIQ), which consists of two subsections of the Stanford-Binet, 5th Edition Intelligence Test. We will also collect the NEPSY-II Affect Recognition and Emotion Guessing Game, as well as Overall Social Interaction (Brief Observation of Social Communication Change, BOSCC). At one of the in-person appointments, we will have participants and consented/assented family members read aloud a script (see section 16) into a microphone to collect audio data to later analyze to help with expression recognition software.

Study Procedures:

First session (Onboarding): Subjects and family members will be asked to come to the [name] Lab at [name] to obtain written or electronic consent. Individuals will meet the study team, will discuss expectations with study manager, discuss how to use the device units, and go over scheduling. Cognitive testing will be conducted in a private assessment where participants will complete the ABIQ. The child/family will then take the Glass home for the duration of the study or we will mail the units home.

Glass at Home: Each participating family will have the Glass units for several weeks during which time the child will use the unit in their own natural environment at home on a daily basis. We will engage on a biweekly to weekly basis (will modify timing if and when necessary) to receive and react to feedback, and then have two-four monthly "in-lab" assessments to monitor improvement of the participant. These checkins can be in person or via a video conference. During the sessions, we will conduct semi-structured and structured interviews to obtain

information about face-gaze, emotion recognition capabilities, and feedback on how the at home sessions are going. We will also collect additional information from the families and participants that they are willing to provide about their experience.

Conclusion: Individuals will come to Stanford to return the units and provide feedback on their experience. They can also mail back their units and have the conclusion session via video conferencing. We will have structured and structured interviews.

Follow up: Study team will connect with participants and families to administer the questionnaires and discuss feedback post study.

We will also have a control population for the study. They will not receive Google Glasses or Android phones. They will only be used as a control group to validate the outcome measures for emotion recognition. A blind study member will evaluate the control population as well as the population with ASD on their ability to recognize facial emotions. They will do this by acting out 8 emotions, 5xs each (Happy, sad, angry, scared, surprised, disgusted, calm, and contempt/meh). We will conduct the emotion recognition evaluation at the checkins for our ASD population and scheduled checkins for our control group. A study team member will meet with the control group, possibly at a social skills class, school, or in their homes, to remain blind to which cohort they are collecting this data from. This emotion recognition component takes about 5 minutes. We will partner with Autism Comprehensive Educational Services (ACES) who offer a variety of behavioral and educational services for individuals impacted with autism or other developmental disabilities in the home, school, community, and at accredited sites throughout the United States. Our main contact will be [redacted], Ph.D., BCBA-D, Chief Clinical Officer, and she will manage the staff from ACES. ACES will help with participant selection:

ACES will help recruit some of our participants. They will screen for participants for IRB 34059 from the population for which they serve. ACES will define and assist in the screening process for eligible participants from said population. They will screen for participants based off of recruitment criteria explained in IRB 34059. Upon selection of participants, ACES will provide contact information to Autism Glass, [name] Lab for which Autism Glass, [name] Lab will officially enroll selected participants into IRB 34059.

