### **3. Statistical Analysis Plan**

This study will follow an intention-to-treat (ITT) analysis, which will include all participants randomized in the study, regardless of missing data. Our hypothesis is that children randomized to receive the Superpower Glass intervention will show a significant improvement on the primary outcome measures, as compared to controls. We will apply a mixed effects

model analysis to assess change from baseline (week 0) to post-test 1 (week 6) in the primary outcome measures.

Primary Outcome Measures:

1. Vineland Adaptive Behavior Scales, 2nd Edition (VABS-II), Socialization subscale
2. Social Responsiveness Scale 2 (SRS-2)
3. NEPSY-II, Affect Recognition subscale
4. Emotion Guessing Game (EGG) scores

Secondary Outcome Measures:

1. Brief Observation of Social Communication Change (BOSCC)
2. Vineland Adaptive Behavior Scales, 2nd edition (VABS-II) Full Scale
3. Child Behavior Checklist (CBCL)

Other measures collected:

1. Stanford-Binet Intelligence Scales, Abbreviated Battery, Fifth Edition (ABIQ)
2. Mobilized Machine Learning Autism Risk Assessment (MARA)
3. Social Communication Questionnaire (SCQ)

We will also perform sensitivity analyses to examine the extent to which outcome measures are correlated to the child's age and autism severity, as well as by usage factors, such as variation in compliance with recommended dosage and missing data from families lost to follow-up. We will use the same approach to assess differences on secondary outcomes between groups using the same mixed effects model analysis. Lastly, we will perform a six-week follow-up analysis on the treatment group to test if a return to baseline occurred.

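### The week-6 model names no covariates and no stratification is specified, so age and baseline autism severity should be prespecified as covariates to recover precision.

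*Combined protocol and SAP*

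**What the plan says.** Section 2 (Study Procedures) sets the randomised sample and the age range: "For n=50 participants, we will run a cross-over design study", and "Participants will be ages 6-12 years old". On allocation it says only that "25 participants will randomly be assigned to group one and continue treatment as usual (control), or group two", which I read as 25 per group. It gives no stratification factor, block size, minimisation scheme or method for generating the sequence.

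Section 3 (Statistical Analysis Plan) analyses all randomised children: "This study will follow an intention-to-treat (ITT) analysis, which will include all participants randomized in the study, regardless of missing data". The hypothesis is that treated children "will show a significant improvement on the primary outcome measures, as compared to controls". The main analysis is a mixed effects "model analysis to assess change from baseline (week 0) to post-test 1 (week 6) in the primary outcome measures". No fixed-effect covariates or random effects are listed. Age and severity enter only later, in "sensitivity analyses to examine the extent to which outcome measures are correlated to the child's age and autism severity"; the same sentence goes on to usage factors and missing data. The SAP does not say which instrument defines autism severity.

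**The concern.** Neither the allocation nor the main model, as written, deals with a chance difference between arms in age or severity. The age range spans 6 to 12 years and the arms are small, so a visible difference on one of these factors would not be surprising. If it occurred and the factor were related to six-week change, the unadjusted comparison would shift for every outcome so related, and any adjustment would have to be chosen after the imbalance had been seen. Even without an unlucky draw, leaving prognostic factors out of the model leaves their variance in the residual, which lowers power in a trial of 50 children.

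**Working it through.** The documents give no alpha, power, effect size, SD or dropout rate, so there is no stated calculation behind n = 50 to reproduce. I assume a two-sided alpha of 0.05, one outcome at a time and no dropout. The correlation ρ of each factor with six-week change is also assumed.

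**1. Chance imbalance at 25 v 25.**
- SE of a standardised baseline difference = √(2/25) = 0.283.
- P(|difference| > 0.5 SD) = 2 × [1 − Φ(0.5/0.283)] = 7.7%. For at least one of two independent factors: 1 − 0.923² = 15%.
- At a threshold of 0.3 SD the same two probabilities are 29% and 49%.
- For a factor split at its median (25 of 50 children), the hypergeometric probability of a 16:9 split or worse is 8.9%.

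**2. Shift in the unadjusted estimate, given an imbalance.** Shift = ρ × imbalance. A 0.5 SD imbalance gives 0.10, 0.15 or 0.25 SD for ρ = 0.2, 0.3 or 0.5. For scale, 25 per arm has 80% power for 0.81 SD (t-based; the normal approximation gives 0.79).

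**3. Type I error of the unadjusted test under simple allocation** (simulation, 10,000 trials per setting, both factors with the same ρ). Over all allocations it is 5.3% at ρ = 0.3 and 5.0% at ρ = 0.5. Among allocations with one factor out of balance by more than 0.5 SD it is about 9% and 16% respectively.

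**4. Power for a true effect of 0.8 SD** (noncentral t).
- Unadjusted: noncentrality 0.8/0.283 = 2.83, 48 df, power 79%.
- Adjusted for two factors, ρ = 0.2 each: residual SD √(1 − 2 × 0.2²) = 0.959, SE 0.271, noncentrality 2.95, 46 df, power 82%.
- Adjusted, ρ = 0.3 each: residual SD √(1 − 2 × 0.3²) = 0.906, SE 0.256, noncentrality 3.12, 46 df, power 86%.
- These adjusted figures take the covariates as balanced. Under simple allocation, estimating two covariate terms inflates the variance on average by 1 + 2/45 = 1.044. The noncentralities fall to 2.89 and 3.06, and power to 81% and 85%.

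**5. What stratification adds** (simulation, ρ = 0.3 each, true effect 0.8 SD, 2 × 2 strata; type I error from the matching runs with no effect).

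| Allocation | Model | SD of estimate | Power | Type I error |
|---|---|---|---|---|
| Simple | Unadjusted | 0.28 | 79% | 5.3% |
| Stratified | Unadjusted | 0.27 | 80% | 3.8% |
| Simple | Adjusted | 0.26 | 85% | 5.3% |
| Stratified | Adjusted | 0.26 | 86% | 5.1% |

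Adjustment gives about six points of power and stratification about one. Stratifying without adjusting makes the test conservative: 3.8% here, and 1.9% at ρ = 0.5.

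**The case against.** The strongest reply is that nothing here is an error. Simple randomisation is valid at n = 50, the estimate is unbiased, and the overall type I error is close to nominal. Modelling change already removes baseline level differences in each outcome, including the SRS-2. What remains depends on how age and severity relate to six-week change, which the documents do not quantify. All of that stands, and it limits the point to precision and to protection against an unlucky draw.

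A reader might infer several stronger things that the documents do not support:
- **That the SAP expects age and severity to predict outcome and then ignores them.** It plans only to examine the extent of correlation, and it names them alongside other items ("age and autism severity, as well as by usage factors").
- **That the trial is run without stratification.** The text is silent on method; it supports only that none is specified.
- **That imbalance would leave thin cells in planned subgroup analyses.** The plan is for correlations, and no age-by-arm or severity-by-arm cells are planned.
- **That stratifying on severity is ready to use.** No section says the SRS-2 is scored before assignment. Section 2 mentions REDCap only for a survey, not for allocation.

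The objection does not remove the gap in the model. The age and severity sensitivity analyses would show whether the factors matter, but they do not prespecify an adjusted treatment comparison.

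**Conclusion.** The point holds as a modest improvement to the SAP. No stratification is specified, the week-6 model names no covariates, and at 25 per arm a difference above 0.5 SD has probability 7.7% for one factor and 15% for at least one of two. The cost of leaving the factors out is precision: for a 0.8 SD effect, about 79% power against 82% to 86% with adjustment (81% to 85% after allowing for covariate imbalance under simple allocation). These figures rest on an assumed correlation of 0.2 to 0.3 for each of two independent factors, two-sided 0.05 and no dropout. With weaker correlations the gain would shrink towards nothing.

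It would be wrong to conclude that the planned comparison is biased or the randomisation invalid, or that stratification is the necessary remedy. The useful change is covariate adjustment.

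**What to change.** **In section 3,** prespecify for each primary outcome that the week-6 mixed model includes age, a baseline severity score and the baseline value of that outcome. Baseline SRS-2 is the natural severity score, since the SAP already needs it to compute change. For the SRS-2 outcome itself, severity and baseline value are then the same term. State how the terms enter: as main effects if week-6 score or change is the response; if both visits are modelled as responses, age and severity need terms that vary by visit, and the baseline should not also be a covariate. Fix this before any outcome data are examined by arm. The cost is two or three degrees of freedom, with no extra children, visits or tests.

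**In section 2,** state how the allocation sequence is generated, and when baseline forms are completed relative to assignment.

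**Optional:** if baseline SRS-2 can be scored before assignment, stratify by age band and a prespecified SRS-2 cut, with random block sizes, and keep both factors in the model. This adds about one point of power. It may move arm sizes a child or two from 25/25 and may require scoring to be brought forward. It should not be done without the matching model terms.

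### Does the aim of judging the device against ABA therapy need changing, given that every randomised child receives ABA?

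*Combined protocol and SAP*

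**What the plan says.** Section 2, Study Procedures, assigns the 50 children at random to "group one and continue treatment as usual (control), or group two and continue treatment as usual plus study procedures (treatment"). The next sentence sets a condition for all of them: "they must receive ABA therapy in the home at least 2xs/week". The one after that states the aim: "We will try to understand the efficacy of the device in comparison to ABA therapy".

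Controls receive the device later. At the week 6 appointment, "Participants will now take device home to use for 6 weeks". In both groups, device sessions may be run with a parent or with the ABA therapist.

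Section 2 also describes a separate control population that gets no device: "They will only be used as a control group to validate the outcome measures for emotion recognition".

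Section 3, Statistical Analysis Plan, expects that "children randomized to receive the Superpower Glass intervention will show a significant improvement on the primary outcome measures, as compared to controls". The planned method is a mixed effects "model analysis to assess change from baseline (week 0) to post-test 1 (week 6) in the primary outcome measures". For the secondary outcomes the plan is to "assess differences on secondary outcomes between groups using the same mixed effects model analysis". Section 3 does not mention ABA.

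**The concern.** The aim names ABA therapy as the comparator, but ABA is present in both arms. A trial of usual care plus device against usual care shows whether the device adds something. It does not show whether the device does better or worse than ABA, or could replace it. These are different claims, and the second would carry more weight with families and payers.

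If the sentence were the operative objective, the trial would have an aim that its design cannot meet. A favourable week 6 result could then be reported as evidence about the device relative to an established therapy. It is also the only sentence in the documents that puts the aim of the randomised comparison in terms of ABA, so a reader might give it more weight than its informal tone suggests.

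**Working it through.** The plan gives no figure to reproduce on this point. The check is whether the literal contrast can be estimated, and whether anything in the planned analysis depends on it.

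**Weeks 0 to 6.** Describe each child by three terms: intercept, ABA, device. From section 2:

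- control: (1, 1, 0)
- treatment: (1, 1, 1)

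The design matrix has rank 2 for 3 parameters. A contrast is estimable only if it is a combination of these two rows, that is, of the form a(1, 1, 0) + b(1, 1, 1) = (a + b, a + b, b).

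- Device added to usual care, (0, 0, 1): a = -1, b = 1 gives it. Estimable.
- Device minus ABA, (0, -1, 1): needs a + b = 0 from the first entry and a + b = -1 from the second. Impossible, so not estimable.
- ABA alone, (0, 1, 0): needs a + b = 0 and a + b = 1. Not estimable.

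**Later periods.** Use five terms: intercept, second six-week period, third six-week period, ABA, device. Code follow-up as device off.

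- group one: (1, 0, 0, 1, 0), (1, 1, 0, 1, 1), (1, 0, 1, 1, 0)
- group two: (1, 0, 0, 1, 1), (1, 1, 0, 1, 0)

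The rank is 4 for 5 parameters. The ABA column equals the intercept column in every row, so the result is unchanged: the add-on effect is estimable and device minus ABA is not. There are 2 planned device periods (group two in weeks 0 to 6, group one in weeks 6 to 12), and neither is planned as ABA-free.

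**Other possible sources of the contrast.** The separate control population has no device and serves only to check the emotion-recognition measures. Section 2 anticipates up to 80 children with ASD, so up to 80 - 50 = 30 fall outside the randomised comparison, and section 3 plans no analysis that sets them against the 50. ABA frequency above the required minimum may vary, but it is not randomised and no analysis uses it.

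**What the arm difference means.** Write A0 and A1 for the effect of ABA as delivered in the control and treatment arms, and D for the device with its study procedures. Then

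treatment - control = (A1 + D) - A0 = D + (A1 - A0).

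It would be too strong to say that ABA simply cancels. Sessions run by the ABA therapist could sit inside ABA time, displace it or add to it, so A1 need not equal A0. The difference is the effect of offering the device, including any change in ABA delivery that the offer causes. That is a proper quantity for the intention-to-treat analysis in section 3. Equal ABA delivery is not needed for it to be valid.

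**What the analysis uses.** Section 3 applies the between-group model to 4 primary + 3 secondary = 7 outcomes. All 7 are compared with controls, and 0 have a device-versus-ABA contrast. None of this depends on the group sizes.

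**The case for a change.** The strongest case for a change is that the three consecutive sentences in section 2 cannot all be taken literally, and that section 3 does not settle the matter because it speaks only of controls and never mentions ABA. One reworded sentence would align the aim with the design at almost no cost and would remove a route to overclaiming.

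Part of this stands. The wording is loose, the literal contrast is out of reach, and a report of this trial should describe the finding as an add-on effect.

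The case does not show that anything would go differently. A reader reaches the sentence having just been told what each arm receives and that all 50 children have ABA, so the natural reading is shorthand for ABA with the device against ABA without it. Section 1 gives the purpose as learning the effects and efficacy of the device and does not speak of outperforming or replacing ABA. Section 3 needs no mention of ABA to be correct, because its controls are the arm already defined in section 2. The overclaim would need someone to set aside both the arm definitions and the stated hypothesis, and no planned analysis would produce a number to support it.

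**Conclusion.** No change to the plan is needed. The observation about the sentence is correct: the trial identifies the effect of offering the device on top of usual care that includes ABA, and it gives no information on the device relative to ABA. The operative parts of the plan already match that. Arms, visits, the 7 outcomes, the model and the sample size would be identical under either wording, so the effect on the primary result is nil. A clearer phrase would be a courtesy to readers and would gain nothing statistically.

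This rests on two assumptions: that the arms are run as section 2 defines them, with ABA continuing in both, and that the results are reported against the hypothesis in section 3. It needs no assumed effect size, and it does not require ABA delivery to be equal in the two arms.

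### Between week 0 and week 6 the plan lists study contact for treatment families only, and the generic home-use text, if it applies to the 50 randomised children, adds questions and tests on the outcome domain in that arm alone.

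*Combined protocol and SAP*

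**What the plan says.** Section 2 randomises 50 children: "For n=50 participants, we will run a cross-over design study where 25 participants will randomly be assigned to group one", with the rest in group two. One group continues treatment as usual; the other continues it with the study procedures added.

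The treatment steps place a six-week device period straight after onboarding and add: "They will have phone calls with study managers to see how usage of the device at home is going". The control steps go from onboarding directly to "come in for an appointment (appointment 1) 6 weeks after onboarding and conduct evaluations again". Then comes "Participants will now take device home to use for 6 weeks", followed by the same sentence about calls. Unstructured interviews are planned in both arms at onboarding and at the six-week visit (conclusion for treatment, appointment 1 for control).

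The Glass at Home paragraph of section 2 is written for every participating family that holds the device. It says: "We will engage on a biweekly to weekly basis (will modify timing if and when necessary) to receive and react to feedback". It adds two to four monthly in-lab assessments, and interviews during the sessions to obtain "information about face-gaze, emotion recognition capabilities, and feedback on how the at home sessions are going". Later in section 2, an acted-emotion test is planned at the check-ins of the ASD population.

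Section 3 plans a mixed effects "model analysis to assess change from baseline (week 0) to post-test 1 (week 6) in the primary outcome measures". The four primaries are VABS-II Socialization, SRS-2, NEPSY-II Affect Recognition and the Emotion Guessing Game (EGG). Section 2 lists the SRS-2 and the Vineland as parent measures, and the NEPSY-II task and EGG as child measures.

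**The concern.** The stated aim in section 1 is the efficacy of the device, and the section 3 hypothesis credits improvement over controls to the Glass intervention. Over the six weeks of that comparison, listed study contact goes entirely with arm. No covariate or model can separate a factor that coincides completely with randomised group, and the section 3 sensitivity analyses (age, severity, usage, missing data) do not touch it.

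Two routes to bias are plausible:

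- **Parent-rated primaries.** Repeated questions about face-gaze and emotion recognition could change how treatment parents score the SRS-2 and VABS-II Socialization at week 6.
- **Child-performed primaries.** Repeated acted-emotion testing could give treatment children practice on a task close to the NEPSY-II Affect Recognition and the EGG.

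Both are separate from parents knowing their arm. Unlike that knowledge, they can be removed through the contact script and the timing of tests.

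**Working it through.** The plan states no alpha, power, SD or contact effect for this comparison, so there is no figure of its own to reproduce.

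**Step 1. Listed contact between the two visits, by arm (section 2)**

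| Source | Treatment, weeks 0–6 | Randomised control, weeks 0–6 |
|---|---|---|
| Group steps | Calls on device usage, number not given | None listed; calls start after week 6 |
| Glass at Home, feedback contacts | 6/2 = 3 (every two weeks) to 6/1 = 6 (weekly); 12 if biweekly means twice a week | None: no device held |
| Glass at Home, monthly in-lab assessments | About 1 | None: no device held |
| Interviews at onboarding and at the six-week visit | Yes | Yes |

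The first row holds on the group steps alone. The next two hold only if Glass at Home governs the randomised children.

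**Step 2. Does Glass at Home apply?** For: it is addressed to each family holding the device. Against: its details do not fit the group steps. It gives several weeks against 6 weeks, daily use against at least four sessions a week, and two to four monthly assessments against a single six-week period. The text leaves the matter open.

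**Step 3. How often would outcome-domain questions be put?** The biweekly-to-weekly contacts are for feedback. The interviews are described after the monthly assessments and may belong to those, so the number before week 6 could be about one or as many as the feedback contacts.

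**Step 4. Do the scheduled check-ins of the control group in section 2 restore balance?** No. That group never receives the Glass and serves to validate the emotion-recognition measures. The randomised controls do receive it, after week 6.

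**Step 5. Illustration of size.** Assumptions: 25 per arm, all analysed; two-sided alpha 0.05; no device effect; a contact-only shift of *d* in SD units of the analysed outcome; a simple two-sample t test in place of the mixed model.

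- Degrees of freedom: 25 + 25 − 2 = 48; critical value 2.011.
- Noncentrality: d × √(25/2) = 3.536 d.
- Probability of a significant result favouring the device: P(T > 2.011), with T noncentral t.

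| Assumed d | Noncentrality | False result favouring the device |
|---|---|---|
| 0 | 0 | 2.5% |
| 0.1 | 0.354 | 5.3% |
| 0.2 | 0.707 | 10.3% |
| 0.3 | 1.061 | 17.9% |

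These are per outcome. The right reference for a false claim of benefit is 2.5%, the upper tail, not 5%.

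**The case against.** The strongest reply is that the contrast is a declared choice. Section 2 defines the treatment arm as usual treatment plus the study procedures, and against usual care, help with using a device can properly be part of the package. That stands: the randomised comparison is valid for the package. What remains is that the aim and hypothesis speak of the device, and the plan nowhere says that the effect includes the support.

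The calls in the group steps concern usage only. That also stands. A reader might infer that treatment parents are certainly questioned three to six times on the outcome domain and control parents never. The documents do not support this. The questioning comes only from the generic Glass at Home text, the count may describe feedback contacts rather than interviews, and controls are interviewed at onboarding and at week 6. Only the period between those visits differs.

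The direction is not certain either. Questions about face-gaze could make parents notice deficits as readily as gains. Nor is the practice effect on the EGG established, because the check-in test is not named as the EGG.

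A reader might also conclude that controls need matched calls. That would take 25 × 3 = 75 to 25 × 6 = 150 extra calls and would move the comparator away from treatment as usual. Neutral calls would still differ in content from calls about the device. It is a trade-off, not a clear improvement.

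**Conclusion.** The concern holds in a limited form. That study-manager contact is unequal in weeks 0 to 6 follows from the group steps alone. That questioning and testing on the outcome domain are unequal between the two visits is conditional on Glass at Home and the check-in test applying to the 50 randomised children, which the text suggests but does not settle. If they apply, all four primaries are exposed, two through parent rating and two through practice, and no analysis can undo it.

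The size is unknown. The chance of a false result in favour of the device runs from about 5% to 18% per outcome for an assumed shift of 0.1 to 0.3 SD, against 2.5% with none; no figure in the documents supports any particular shift. A reader might take this as showing that the week-6 comparison is invalid. It does not: the comparison still estimates device plus support against treatment as usual, but any outcome-domain questioning or testing confined to one arm would add a measurement difference that is no part of either.

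**What to change.** 1. Reconcile the group steps and the Glass at Home text for the 50 randomised children. State which contacts, interviews and tests occur in each arm between onboarding and the six-week visit, and how often.
2. In weeks 0 to 6, limit treatment-arm contacts to technical and usage questions. Hold all interview questions and tests on face-gaze, emotion recognition and social behaviour until the week-6 outcome measures are complete in both arms. At the six-week visit itself, run the outcome measures before the unstructured interview.
3. State in section 3 that the week-6 contrast estimates the device plus usage support against treatment as usual.

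The cost is wording in the procedures and call scripts, and some in-use feedback on emotion recognition is delayed to week 6. No added visits or calls are needed. These changes do not address parents' knowledge of arm, which remains a separate limitation of the parent ratings.
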